#### **4. Duration of response (DoR)**

Duration of response is defined as the time from the date of first documented overall response of confirmed CR or PR until date of first documented progression or death (from any cause), whichever occurs first. The first date at which a CR or PR response was noted will be used to calculate DOR, not the

date of the confirmatory tumor assessment. Unconfirmed response will not be included.

Patients who do not experience disease progression or death following a response at the time of analysis will be censored at the date of last tumor assessment by RECIST 1.1 criteria.

Duration of response will only be evaluated for patients who have a best overall response of CR or PR.

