To be considered a PR or CR in the clinical trial report, changes in tumour measurements must be confirmed by repeat assessments that should be performed no less than 4 weeks after the criteria for response are first met.

Stable disease is defined as neither sufficient shrinkage to qualify for PR nor sufficient increase to qualify for PD. In the case of SD, follow-up measurements must have met the SD criteria at least once after study entry at a minimum interval of not less than 35 days.

When the Investigator is in doubt as to whether progression of disease has occurred and therefore reassesses the patient at a later date, the date of the initial scan should be declared as the date of progression if the repeat scans confirm progression.

For further details see Appendix 4

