### **Duration of response**

Duration of response will be defined as the time from the date of first documented response until date of documented progression or death in the absence of disease progression, the end of response should coincide with the date of progression or death from any cause used for the PFS endpoint. The time of the initial response will be defined as the latest of the dates contributing towards the first visit response of PR or CR.

If a subject does not progress following a response, then their duration of response will use the PFS censoring time.

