### **Progression Free Survival**

Progression-free survival (PFS) will also be assessed. Analyses will be done at the RP2D and pooled for all patients in a module.

Progression free survival (PFS) is defined as the time from start of treatment (first dose of RXC004, or combination agent if relevant, whichever is first) until the date of objective disease progression or death (by any cause in the absence of progression) regardless of whether the subject withdraws from therapy or receives another anti-cancer therapy prior to progression.

Patients who have not progressed or died at the time of analysis will be censored at the time of the latest date of assessment from their last evaluable RECIST assessment. However, if the patient progresses or dies after two or more missed visits, the patient will be censored at the time of the latest evaluable RECIST assessment. If the patient has no evaluable visits or does not have baseline data they will be censored at 0 days unless they die within two visits of baseline.

The PFS time will always be derived based on scan/assessment dates not visit dates.

RECIST assessments/scans contributing towards a particular visit may be performed on different dates. The following rules will be applied:

- Date of progression will be determined based on the earliest of the dates of the component that triggered the progression
- When censoring a subject for PFS the subject will be censored at the latest of the dates contributing to a particular overall visit assessment

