#### **5. Progression Free Survival (PFS)**

Progression free survival (PFS) is defined as the time from the date of first study treatment (first dose of RXC004 or Nivolumab if relevant, whichever is first) until the date of objective disease progression or death (by any cause in the absence of progression) regardless of whether the patient withdraws from study treatment or receives another anti-cancer therapy prior to progression/death. Date of progression will be determined based on the date of first radiological assessment indicating progression (i.e., first scan date when an overall response is determined to be progressive disease as assessed by the investigator per RECIST overall response CRF page).

Patients who have not progressed or died at the time of analysis will be censored at the time of the latest date of scan/assessment from their last evaluable RECIST assessments. However, if the patient progresses or dies after two or more missed visits, the patient will be censored at the time of the latest evaluable RECIST scan/assessment prior to the missed visits. If the patient has no evaluable visits or does not have baseline data, they will be censored at 1 day unless they die within 2 scan visits of baseline.

Lesion parameters will be assessed at each RECIST assessment, including target lesion diameter (for lymph nodes, the shortest diameter will be collected; for soft tissue lesions, the longest diameter will be collected), presence/absence of non-target lesions; and presence/absence of new lesions.

The sum of the diameter of target lesions will be calculated at each RECIST assessment. Change and percent change from baseline in the sum of diameter of TLs will also be calculated.

The best percentage change in tumor size while on treatment will be the patient's value representing the largest decrease (or smallest increase for those patients whose target lesions do not show a decrease) from baseline in the sum of diameter of TLs.

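### SAP VIII.A.4 ends and censors DoR by rules separate from PFS, against protocol 9.2.1, and SAP VIII.A.5 omits the protocol's back-dating of confirmed doubtful progressions

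*SAP*

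**What the plan says.** **End of response.** Protocol 9.2.1 (Duration of response) says that "the end of response should coincide with the date of progression or death from any cause used for the PFS endpoint". It adds: "If a subject does not progress following a response, then their duration of response will use the PFS censoring time". SAP VIII.A.4 runs DoR from the first confirmed CR or PR "until date of first documented progression or death (from any cause), whichever occurs first". Responders with neither event "following a response at the time of analysis will be censored at the date of last tumor assessment by RECIST 1.1 criteria". That section does not mention PFS or missed visits.

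**PFS censoring.** Protocol 9.2.1 (Progression Free Survival) and SAP VIII.A.5 share the missed-visit rule; in the SAP's words, "if the patient progresses or dies after two or more missed visits, the patient will be censored". The censoring date is that of the latest evaluable assessment, and the SAP specifies the one before the missed visits.

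**Date of progression.** Protocol 7.1 tells an investigator who doubts whether progression has occurred to reassess at the next scheduled scan, or earlier if clinically indicated. It then says that "the date of the initial scan should be declared as the date of progression if the repeat scans confirm progression". SAP VIII.A.5 defines the progression date as the "first scan date when an overall response is determined to be progressive disease as assessed by the investigator" on the RECIST CRF page. It has no back-dating rule.

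**Use.** SAP VIII.B plans Kaplan-Meier summaries of both PFS and DoR, and swim-lane plots that show them. It does not summarize DoR for Module 3.

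**The concern.** The protocol makes DoR a by-product of PFS: one end date and one event status per patient. The SAP gives adjacent endpoints different censoring rules. A programmer following it would give the same patient opposite statuses in two Kaplan-Meier analyses, and the swim-lane plots would show the conflict. The protocol wording excludes this result, and the SAP does not present it as a deliberate change.

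The dating gap is a second departure. Where doubt is resolved as progression, the protocol wants the earlier date. The SAP's literal rule gives the later one whenever the earlier scan stays recorded as something other than PD. Any such shift lengthens that patient's PFS, and with few patients one date can move a median.

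**Working it through.** The plan gives no figure to reproduce, so the check traces hypothetical patients through the written rules.

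**Inputs**
- Scan interval from Cycle 1 Day 1: 6 weeks (42 days) in Modules 1 and 3, 8 weeks (56 days) in Module 2 (protocol Appendices 1, 9 and 2).
- Cycle 0 lead-in: 6 to 10 days in Module 1, 3 to 7 days in Modules 2 and 3 (same appendices).
- Study day 1 is the first dose (SAP VI.E), so the study day of scan k = k × interval + lead-in + 1.
- DoR in days = end − first response + 1. The SAP states no DoR formula; the +1 follows its convention elsewhere and is an assumption.

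**Patient A: PR at scan 1, confirmed at scan 2, scans 3 and 4 missed, PD at scan 5**

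| | Module 2 | Module 1 |
|---|---|---|
| PFS (protocol and SAP): censored at scan 2 | 112 + 3 + 1 = day 116, to 112 + 7 + 1 = day 120 | 84 + 6 + 1 = day 91, to 84 + 10 + 1 = day 95 |
| DoR, SAP: **event** at scan 5 | 4 × 56 + 1 = 225 days (about 32 weeks) | 4 × 42 + 1 = 169 days |
| DoR, protocol: **censored** at scan 2 | 56 + 1 = 57 days (about 8 weeks) | 42 + 1 = 43 days |

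The protocol row rests on this reading: no progression date is used for this patient's PFS, so the end of response can only be the PFS censoring date.

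**Patient B: PR at scans 1 and 2, scan 3 not evaluable, nothing later**

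SAP DoR is censored at the last assessment, scan 3: 2 × 56 + 1 = 113 days in Module 2, or 2 × 42 + 1 = 85 days in Module 1. PFS is censored at scan 2, which corresponds to a DoR of 57 or 43 days. This assumes that a non-evaluable scan counts as a tumour assessment, as the SAP's DoR wording allows.

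**Direction of the DoR effect (Module 2, whole weeks)**
- Patient A alone: under the protocol the curve never falls. Under the SAP it falls to 0 at 40 − 8 = 32 weeks, so the SAP is less favourable.
- Add a responder with PR at weeks 8 and 16 and PD at week 24, a DoR of 24 − 8 = 16 weeks. Under the protocol, patient A is censored at 8 weeks, one patient is at risk at 16 weeks, and the curve falls to 0. Under the SAP, two are at risk, and the curve is 1/2 from 16 to 32 weeks, so the SAP is more favourable over that stretch.

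The sign depends on the other responders.

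**Patient C: scan 2 doubtful and recorded as not PD, PD at scan 3**

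| Module | Protocol date (scan 2) | SAP date (scan 3) | Shift |
|---|---|---|---|
| 1 | day 91–95 | day 133–137 | 42 days |
| 2 | day 116–120 | day 172–176 | 56 days |
| 3 | day 88–92 | day 130–134 | 42 days |

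These are upper limits, because an unscheduled repeat scan shortens the shift. If the scan 2 entry is revised to PD, the shift is zero.

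**The case against.** **Materiality.** Efficacy is a preliminary secondary objective with no hypothesis test. DoR is not summarized for Module 3, and protocol 9.5 plans it only if there are enough responses. The Module 1 account in protocol 1.7.1.1 gives stable disease in 5 of 18 evaluable patients and mentions no response. Module 2 planned about 18 patients, and SAP Table 2 shows two of its three dose levels run. The conflict also needs a confirmed responder who misses two scans and then progresses or dies, or whose last scan is not evaluable. All of this stands and limits the size of the point.

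**The SAP need not repeat the protocol.** Its Introduction says that it will not restate every definition. That would cover silence, but here the SAP states its own, different rules.

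**Dating depends on the CRF.** If the investigator declares the initial scan as the progression and the CRF shows it, the two documents agree. This stands, so the dating limb is conditional.

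**Stronger readings a reader might infer**
- *That a DoR longer than PFS is an impossible result.* PFS censored at day 116–120 means at least that long, and a 225-day DoR event does not contradict it. The fault is two event conventions for one patient.
- *That every efficacy endpoint is flattered.* A late event replacing an early censoring can lower the DoR curve, as shown above. Only the dating gap has a fixed direction.
- *That DCR also departs from the protocol.* The SAP's DCR rule follows protocol 9.2.1 with Module 3 added, and protocol 7.1 moves a progression date without reclassifying a visit response. Nor does one patient in six (16.7 points) measure the effect: DCR is defined over all patients dosed, while six is the number of evaluable patients per Module 3 arm.

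**Conclusion.** The DoR limb holds on the text without conditions: SAP VIII.A.4 departs from protocol 9.2.1, and nothing elsewhere repairs it. In the traced Module 2 case the SAP gives a 225-day event where the protocol gives censoring at 57 days; a final non-evaluable scan gives censoring at 113 days instead of 57. The effect on the DoR curve has no predictable sign. The practical reach is mainly Module 2.

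The dating limb holds conditionally. A doubtful progression that is later confirmed can be dated up to 6 weeks late in Modules 1 and 3, or up to 8 weeks late in Module 2, if the doubtful scan's CRF entry is not revised. It can affect PFS in every module.

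The figures assume scans exactly on schedule and the +1-day convention. The documents do not say how often such patients occur, so no effect on a median or rate is claimed. This is a consistency correction to descriptive secondary endpoints.

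**What to change.** - **SAP VIII.A.4:** state that the DoR end date and event or censoring status are those of the patient's PFS, as protocol 9.2.1 requires. This brings in both the missed-visit rule and the last-evaluable-assessment rule.
- **SAP VIII.A.5:** add that when a repeat scan confirms a progression that was in doubt, the progression date is that of the initial scan, as in protocol 7.1. Leave the DCR and BOR visit-response rules as they are.

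If either departure is intended, say so in the SAP and give the reason.

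The cost is two sentences, a small programming change, and a check that the CRF or a data query can identify doubtful scans. The SAP Introduction indicates that the Module 1 database was already locked, so any change to Module 1 results would be recorded as a deviation in the study report, as that section provides.

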#### **5. Progression Free Survival (PFS)**

Progression free survival (PFS) is defined as the time from the date of first study treatment (first dose of RXC004 or Nivolumab if relevant, whichever is first) until the date of objective disease progression or death (by any cause in the absence of progression) regardless of whether the patient withdraws from study treatment or receives another anti-cancer therapy prior to progression/death. Date of progression will be determined based on the date of first radiological assessment indicating progression (i.e., first scan date when an overall response is determined to be progressive disease as assessed by the investigator per RECIST overall response CRF page).

Patients who have not progressed or died at the time of analysis will be censored at the time of the latest date of scan/assessment from their last evaluable RECIST assessments. However, if the patient progresses or dies after two or more missed visits, the patient will be censored at the time of the latest evaluable RECIST scan/assessment prior to the missed visits. If the patient has no evaluable visits or does not have baseline data, they will be censored at 1 day unless they die within 2 scan visits of baseline.

Lesion parameters will be assessed at each RECIST assessment, including target lesion diameter (for lymph nodes, the shortest diameter will be collected; for soft tissue lesions, the longest diameter will be collected), presence/absence of non-target lesions; and presence/absence of new lesions.

The sum of the diameter of target lesions will be calculated at each RECIST assessment. Change and percent change from baseline in the sum of diameter of TLs will also be calculated.

The best percentage change in tumor size while on treatment will be the patient's value representing the largest decrease (or smallest increase for those patients whose target lesions do not show a decrease) from baseline in the sum of diameter of TLs.

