In Module 1, 5/18 RECIST-evaluable patients had SD, in one case lasting for up to 26 weeks. All five of these patients had Wnt-ligand-dependent tumours. None of the patients with Wnt ligand-independent tumours had SD. Following this observation, Module 3 (intermittent monotherapy doses) was designed to enrol only patients with Wnt ligand-dependent tumours to receive RXC004 monotherapy, in order for patients to have the best chance of experiencing clinical efficacy.

Potential patients will be fully informed of the risks and requirements of the study. During the study patients will be given any new information that may affect their decision to continue participation. They will be informed that their consent to participate in the study is voluntary and may be withdrawn at any time with no reason given and without penalty or loss of benefits to which they would otherwise be entitled. Only patients who are fully able to understand the risks, benefits, and potential AEs of the study, and provide their consent voluntarily will be enrolled.

Please refer to IB for further information.

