### 5.4.3 Dose Rationale

In Module 3, intermittent schedules of RXC004 will be investigated. The intermittent schedules will use 2mg QD RXC004, which has already shown to be safe and tolerated when used continuously in Module 1 of this study. This dose delivers Cmin values > 3-fold IC50 in patients, which is expected to lead to >50% Wnt pathway inhibition, while also being safe and tolerable.

Module 1 opened in 2018 with a RXC004 dose of 10mg once daily, but the dose was not tolerated in the first patient and the Module 1 dose escalation was restarted on 18th March, 2019 with 0.5mg RXC004. As of the 30th July, 25 patients have been dosed with RXC004 monotherapy in Module 1 of the study at doses of 0.5mg (4), 1mg (3), 1.5mg (7), 2mg (6), 3mg (4) and 10mg (1)

At doses up to and including 2 mg QD, the most common treatment related AEs were fatigue (10/20 patients), nausea (7/20), decreased appetite (6/20), dysgeusia (6/20), and vomiting (4/20). Of these, only dysgeusia appeared to be dose related. No Grade 4/5 treatment related AEs or bone fragility events were reported at any of these dose levels of RXC004.

A detailed description of the RXC004 risks is provided in Section 1.7.1. Details of the pharmacology, efficacy, and safety of RXC004 is also provided in the RXC004 Investigator's Brochure.

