## Analysis Populations

Four analysis populations will be defined for use with various analyses.

- The Safety Population will consist of all patients who enrolled and receive at least one dose of study drug.
- The PK Evaluable Population will consist of those patients deemed by the sponsor or pharmacokineticist to have sufficient PK concentration data to be meaningfully included in the PK analysis summaries.
- The PD Evaluable Population will consist of those patients deemed by the sponsor or translational scientist to have sufficient PD assessment data to be meaningfully included in the PD analysis summaries.
- The Efficacy Evaluable Population will include patients who receive a radiographic assessment at baseline, received at least one dose of study treatment, and at least one post-dose radiographic tumour assessment, or progressed ahead of the first scan.

Adverse events and medical history will be coded using the Medical Dictionary for Regulatory Activities (MedDRA) version 20.0 or greater. Concomitant medications will be coded using the World Health Organization Drug Dictionary (WHODrug: March 2017 or later version).

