### **2. Efficacy Evaluable Population**

The Efficacy Evaluable Population will include patients who receive a radiographic assessment at baseline, received at least one dose of any study treatment, and at least one post-dose radiographic tumor assessment, or progressed or died ahead of the first scan. The efficacy evaluable population will be used for the efficacy analyses.

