# **VIII. Efficacy Analyses**

Efficacy analyses will be based on the Efficacy Evaluation Population.

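### A patient who progresses before the first scan, never has an evaluable scan and outlives two scan visits is in the efficacy population but is censored at Day 1 for PFS

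*SAP*

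**What the plan says.** **Population.** SAP VI.J.2 requires a baseline radiographic assessment, at least one dose, and then "at least one post-dose radiographic tumor assessment, or progressed or died ahead of the first scan". The protocol (section 9.2, Analysis Populations) has "at least one post-dose radiographic tumour assessment, or progressed ahead of the first scan", without naming death. SAP VIII states "Efficacy analyses will be based on the Efficacy Evaluation Population", so this population carries PFS.

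**PFS event.** SAP VIII.A.5 runs PFS from first treatment "until the date of objective disease progression or death (by any cause in the absence of progression"). The progression date is the first scan date on which the investigator's RECIST overall response is progressive disease.

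**PFS censoring.** For patients with no evaluable visit or no baseline data, the SAP rule is "they will be censored at 1 day unless they die within 2 scan visits of baseline". Protocol 9.2.1 has the same rule and the same exception for death, but censors at 0 days.

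**DCR.** SAP VIII.A.3 takes all dosed patients as the denominator and requires at least stable disease at the second scheduled scan. A missing second scan is rescued only by a later evaluable response of stable disease or better.

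**Reporting.** SAP VIII.B gives the Kaplan-Meier median and PFS at 6 and 12 months with 95% confidence intervals, for the RP2D and overall. No sensitivity analysis of PFS is planned.

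**The concern.** The population definition names two kinds of early failure, progression and death before the first scan. The exception in the PFS censoring rule covers only death. For a patient with no scan, progression ahead of the first scan cannot be radiological, so it can never be a PFS event as defined. If that patient is never evaluably scanned and lives past two scan visits, the patient is censored at Day 1. A death after that point does not change this.

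Kaplan-Meier assumes that censored patients have the same outlook as those still at risk. Here the scan is missing because the patient failed early, so the assumption fails in a known direction and PFS can come out too favourable. The same patient is a failure for DCR and contributes nothing to PFS, so the two endpoints in one report would describe different groups. In cohorts of about six, one or two such patients are enough to change what a reader sees.

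**Working it through.** The plan states no PFS figure that depends on this rule, so there is nothing to reproduce. The check is to identify who is affected and then to size the effect.

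**1. Who is affected**

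Baseline imaging is a condition of entry to the population, so only the no-evaluable-visit branch of the censoring rule matters. Scans are every 6 weeks in Modules 1 and 3 and every 8 weeks in Module 2 (Protocol Appendices 1, 9 and 2). Two scan visits are therefore about 2 x 6 = 12 weeks or 2 x 8 = 16 weeks.

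| Patient who progresses before the first scan | PFS under the SAP | DCR |
|---|---|---|
| Dies within two scan visits, never scanned | Event at death | Failure |
| Scanned later, scan shows progression | Event at scan date (unless two or more visits were missed first) | Failure |
| Never evaluably scanned, alive past two scan visits | **Censored at Day 1** | Failure |

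Only the last row is at issue. Let k be the number of such patients among N.

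**2. Formula**

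Patients censored at Day 1 leave before any plausible event, so the SAP curve is that of the other N-k patients alone, S(t). If the k patients are instead events before anyone else has an event, the curve first falls to (N-k)/N and then follows S(t) from there:

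S_alt(t) = S(t) x (N-k)/N

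- N = 25: k = 1 gives 24/25 = 0.96; k = 7 gives 18/25 = 0.72.
- N = 6: k = 1 gives 5/6 = 0.83; k = 2 gives 4/6 = 0.67.

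**3. Range of k in Module 1**

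Protocol 5.4.3: "25 patients have been dosed with RXC004 monotherapy in Module 1". Protocol 1.7.1.1: "In Module 1, 5/18 RECIST-evaluable patients had SD". So 25 - 18 = 7 were not RECIST-evaluable. The reasons are not given, and k lies between 0 and 7.

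**4. Illustration, Module 1**

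Assume that the 13 evaluable patients without stable disease progressed at week 6, that the 5 with stable disease progressed later (two of them at week 12), and that the k patients progressed on day 28. PFS just after week 6:

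| k | SAP rule | k counted as events |
|---|---|---|
| 0 | 5/18 = 27.8% | 27.8% |
| 1 | 27.8% | 5/19 = 26.3% |
| 3 | 27.8% | 5/21 = 23.8% |
| 5 | 27.8% | 5/23 = 21.7% |
| 7 | 27.8% | 5/25 = 20.0% |

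The SAP estimate is the same whether k is 0 or 7. The median is week 6 in every row.

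The exception for death limits the loss. With 7 never-scanned patients, 12-week PFS is 3/25 = 12.0% under both rules if all 7 die within 12 weeks. If none die, it is 3/18 = 16.7% under the SAP rule against 12.0%.

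**5. Illustration, one Module 3 arm of 6**

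Assume exponential progression times with a 12-week median in the scanned patients, detected at 6-weekly scans.

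| k of 6 | 12-week PFS, SAP rule | 12-week PFS, k as events | Median |
|---|---|---|---|
| 1 | 2/5 = 40.0% | 2/6 = 33.3% | week 12 under both |
| 2 | 2/4 = 50.0% | 2/6 = 33.3% | week 12 becomes week 6 |

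**The case against.** **Objective-only PFS is a deliberate choice.** Both documents define it that way, and in an open-label, non-comparative study progression declared without a scan is a judgement. This stands, and is why the main analysis should not change.

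**Follow-up closes much of the gap.** Protocol 7.1 stops imaging only at objective progression, section 3.6 follows patients off drug until progression, and the schedules run scans until RECIST progression. A reader might infer that all early failures vanish from the curve. The documents do not support that, as the first table above shows. The gap is not fully closed: section 7.1 asks for continued scans after stopping for reasons other than progression, so patients stopped for clinical progression are not clearly covered.

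**The Module 1 count may have nothing to do with this.** A reader might infer that 7 of 25 were lost this way, or that the plan would report 28% instead of 20%. Neither is supported. The RECIST-evaluable group is not defined as the SAP's efficacy population, and 5/18 is a count of stable disease, not a planned PFS estimate. Toxicity is another possible reason: 10 mg was not tolerated in the first patient, and colitis or enteritis occurred in four patients starting at 3 or 10 mg (Protocol 5.4.3, Appendix 5). A never-scanned patient who stopped for toxicity without progressing is outside the efficacy population altogether.

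**The reported summaries may barely move.** The Module 1 median stays at week 6 in the illustration. The one stable-disease duration cited is up to 26 weeks. If that is the longest, 6-month PFS is at most about 1/18 = 5.6% against 1/25 = 4.0%, and 12-month PFS is near zero either way. This stands for Module 1, but not necessarily for an arm of six.

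**Affected patients are visible elsewhere.** Discontinuation reasons are tabulated, efficacy data are listed, and swim-lane plots are planned. True, but none of this gives the number censored at Day 1 next to the PFS estimate.

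**Conclusion.** The point holds for one subgroup: patients in the efficacy population because they progressed before the first scan, with no evaluable post-baseline scan and no death within two scan visits. For them the population and censoring rules do not fit together, the censoring is informative, and DCR and PFS disagree. That the progression is clinical is an inference, but it follows when there is no scan.

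The size is the factor (N-k)/N on estimates after the first scan, given that the k failures precede all other events. It is 0.96 to 0.72 for k = 1 to 7 of 25 and 0.83 to 0.67 for k = 1 to 2 of 6. The documents do not give k, and it may be zero. A reader might go further and conclude that the median and the 6- and 12-month figures are biased upward. The documents do not establish that; these may or may not move.

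PFS is a secondary, descriptive endpoint with no hypothesis test, so no error rate or sample size is affected. Minor; a cheap improvement.

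**What to change.** - Keep the RECIST PFS as the main analysis.
- Add one supportive Kaplan-Meier analysis in which stopping treatment for disease progression before any evaluable scan is an event on the recorded discontinuation date. The documents neither define clinical progression nor say that its date is captured, so the discontinuation record is the practical source. Confirm on the eCRF that the reason and date are available.
- Beside both analyses, report the number censored at Day 1, with reasons. If it is zero, that shows PFS is unaffected.
- Align the protocol's 0 days with the SAP's 1 day.
- Prespecify this for any module not yet locked. The SAP Introduction says Module 1 was already locked when the Module 2 and 3 changes were made, so label any Module 1 run post hoc.

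**Cost.** A few lines of SAP text and one extra run; SAP VII.C already summarises discontinuation reasons. The supportive estimate relies on investigator-judged progression and, if k is above zero, will be slightly less favourable.
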